6.9 COVID-19

The impact of COVID-19 infection on SAA patients with marked neutropenia and with immunosuppressive treatment is currently unknown. Known risk factors include high age, and comorbidities particularly heart and lung disease. Data is limited and conflicting regarding the risks in immunosuppressed patients. Following treatment guidelines are made with current available information and may be amended with future evidence. Patients will be monitored with clinical vigilance and expedited testing in suspected cases.

- All patients will be educated on preventative practices.
- PCR test for SARS-CoV2 and respiratory viral panel will be performed in patients with fever, upper or lower respiratory tract symptoms.
- In patients with mild COVID-19 infection, lower dose CSA and EPAG treatment will not be delayed.
- In patients with severe COVID-19 infection, lower dose CSA and EPAG treatment may be delayed per PI discretion.
- Standard of care treatment (h-ATG, higher dose CSA and EPAG), which is more immunosuppressive than lower dose CSA, will be delayed at least 2 weeks from the diagnosis of COVID-19 and may be longer in severe cases based on their clinical condition.

7 CRITERIA FOR RESPONSE/CLONAL EVOLUTION/RELAPSE

Misdiagnosis is defined as diagnosis of other hematological or non-hematological condition to explain peripheral pancytopenia.

Non-compliance for feasibility is defined as not following up at the Clinical Center by 8 weeks (or within allowed grace period in special circumstances defined in section 9.6) or failure to comply with the recommended oral treatment or clinical/laboratory assessment.

Response is defined as blood counts no longer meeting the standard (“Camitta”) criteria for severe pancytopenia in SAA (Section 4.1), equivalent to 2 of the following values obtained on 2 serial blood count measurements at least one week apart at landmark time points (2, 3, and 6 months).

- Absolute neutrophil count $\geq 500/\mu\text{L}$
- Platelet count $\geq 20,000/\mu\text{L}$
- Reticulocyte count $\geq 60,000/\mu\text{L}$

A **complete response (CR)** will be defined as (all 3 must be met):

- Absolute neutrophil count $\geq 1,000/\mu\text{L}$
- Platelet count $\geq 100,000/\mu\text{L}$
- Hgb $\geq 10\text{ g/dL}$

Abbreviated Title: Early Initiation of Oral Therapy for Naïve Severe Aplastic Anemia (SAA)

Version Date: 11/05/2025

A **partial response (PR)** will be defined as blood counts that do not meet criteria for severe pancytopenia but are not sufficient for a CR.

Improvement in counts that are dependent upon exogenously administered growth factors or transfusion will not be considered as fulfilling response criteria.

Clonal Evolution: The presence of evolution to PNH will be defined by flow cytometric detection of > 1% GPI-deficient neutrophils at baseline and landmark time points through 5 years (only the ones where patient is evaluated at the Clinical Center, excludes months 1 and 2). Evolution to hyperproliferative/dysplastic myelodysplasia and/or acute leukemia will be assessed at landmark time points, or as clinically indicated between landmarks by examination of peripheral blood and bone marrow based on diagnosis and classification according to the WHO 2016 criteria. Evolution to clonal hematopoiesis will be defined by detection of new bone marrow cytogenetic abnormalities at landmark time points.

Relapse:

In this protocol, relapse is defined as having, EITHER,

1. Blood count decline to a degree where they again meet “Camitta” criteria (see Section 4.1) for severe aplastic anemia determined from at least 2 blood count measurements done within 14 days, or
2. Progressive decline in one or more blood counts, not explained by another clinical process (e.g. acute infection or medication related) determined from at least 2 blood count measurements done within 14 days.

The date of relapse will be recorded into the clinical database as the date the participant resumed immunosuppression with CsA or required higher doses of CsA if on the low dose prior to the 2-year landmark visit, resumed EPAG or h-ATG (if subject had not received h-ATG previously), or proceeded with another treatment for SAA.

A description of how the clinical assessment was made by the PI will be recorded in the clinical database. To corroborate the relapse, the most recent blood counts collected prior to the date of relapse will be recorded into the clinical database with the following parameters: absolute neutrophil count, or neutrophil percentage and white blood cell count if ANC is not available, hemoglobin, absolute reticulocyte count (or reticulocyte percentage and RBC if absolute reticulocyte count is not available) and platelets.

8 EXPLORATORY LABORATORY RESEARCH STUDIES

Intended use: During the course of participating on this study, additional 60 cc of blood (3 ml/kg not to exceed 60 ml of blood for pediatric subjects) at first visit to the Clinical Center and at landmark visits at 3, 6, 12 months and annually thereafter, and 15 ml of bone marrow aspirate (prior to ATG, 3 months, 6 months, 12 months, and annually thereafter) may be obtained for correlative laboratory research studies. Up to an additional 10 cc of blood may be collected during follow up every 1-6 months (according to how often they get their counts checked) for correlative laboratory studies. The protocol will cover shipment materials/costs for these additional samples to be returned to the NIH since they are for research use (no results given). Initial samples collected upon first visit at the Clinical Center may be obtained on another protocol, such as 04-H-0012. These studies are not used in assessing the primary endpoint but

Abbreviated Title: Early Initiation of Oral Therapy for Naïve Severe Aplastic Anemia (SAA)

Version Date: 11/05/2025

are undertaken as descriptive or exploratory ancillary studies as listed below. Some or all may be performed on each subject, and they may be correlated with response.

- Thrombopoietin level
- CD34 cell number in whole blood and bone marrow aspirate by flow cytometry
- T cell receptor V-beta profile in the marrow and peripheral blood
- Extended peripheral blood flow cytometric phenotyping for cell surface or intracellular proteins
- Evaluation for the presence of abnormalities of the telomere repair complex including telomere length, DEB testing for Fanconi anemia.
- Evaluation for the presence of abnormalities of genes associated with hematopoiesis, via genetic testing or gene expression analysis.
- Evaluation for the presence of abnormalities of genes associated with inherited bone marrow failure or inborn errors of immunity.
- Serum cytokine, chemokines and soluble receptor levels
- Serum (or plasma) and cells for viral analyses
- Hematopoietic progenitor colony, long term-culture-initiating cell, and immunodeficient mouse engraftment assays for primitive cell content and function
- Single cell RNAseq or multi-omics on bone marrow specimens to detect chromosomal aneuploidy before and after treatment.
- Telomere length on peripheral blood leukocytes by flow-FISH before and after treatment

9 BIOSTATISTICAL CONSIDERATIONS

9.1 PRIMARY ENDPOINTS

The primary endpoint of this pilot study is to evaluate the safety and feasibility of rapid initiation of oral treatment regimen, CsA + EPAG prior to receiving standard regimen at the Clinical Center in treatment naïve SAA as a composite measure of the following:

- Rates of TRSAE (treatment related serious adverse events) compared to standard regimen (protocol 12-H-0150). TRSAE are defined in section 9.5.
- Rates of mis- and altered diagnoses compared to standard regimen. **Misdiagnosis** is defined as diagnosis of other hematological or non-hematological condition to explain peripheral pancytopenia such as myeloid neoplasm.
- Number and proportion of patients who are unable to comply with the outpatient early drug regimen and withdraw from study or who do not present to the Clinical Center for evaluation within 8 weeks (or within allowed grace period in special circumstances defined in section 9.6)

9.2 SECONDARY ENDPOINTS

Secondary endpoints will be: (a) hematological response at 1, 2, 3, 6 and 12 months and yearly thereafter; (b) relapse; (c) clonal evolution to PNH, clonal chromosomal population in bone marrow, myelodysplasia by morphology, or acute leukemia; (d) overall survival; (e) hematological response of relapse subjects that re-start treatment with cyclosporine and/or eltrombopag; (f) freedom from h-ATG.

Abbreviated Title: Early Initiation of Oral Therapy for Naïve Severe Aplastic Anemia (SAA)

Version Date: 11/05/2025

Subjects will be followed up to 60 months so that long-term disease-free and overall survival can be estimated. Response and toxicity comparisons will be made with previous IST combined with eltrombopag protocol (12-H-0150)

9.3 SAMPLE SIZES AND STATISTICAL DESIGN

Cohort 1: Since safety and feasibility is defined in Section 9.1 to be the primary endpoint of this study, the treatment is defined to be “feasible” to a patient if he/she meets the safety and feasibility criteria specified in Section 9.1 at the end of study treatment period. Study treatment period is defined as the duration from the initiation of oral treatment to the start of standard of care treatment here at NIH. “Feasibility” is defined as tolerating treatment without the composite of TRSAE/misdiagnoses/noncompliance (defined in section 9.1). Our past experience with the standard 3 drug regimen (12-H-0150) suggests that the probability of feasibility for this patient population is approximately 90%. We hypothesize that the actual feasibility probability using this novel treatment paradigm may decrease to 75%, therefore a probability of 75% or less would warrant terminating this novel treatment approach. The hypotheses are equivalent to $H_0: p \leq 75\%$, in which feasibility is unacceptable, and $H_1: p \geq 90\%$, in which feasibility is acceptable. Our sample size is determined by testing this hypothesis at a significance level of 0.05 and 0.80 power. We intend to test this treatment approach using a small number of patients and terminate the study if early evidence suggests that the feasibility probability diminishes below the benchmark of 75%. We determine the sample size using the Two-Stage Minimax Design of Simon (1989), since it requires a smaller total number of subjects ($n = 39$) compared to the Two-Stage Optimal Design ($n = 48$). At the first stage, 22 subjects will be accrued, and the null hypothesis will be accepted if 17 or fewer subjects are determined to be feasible to the treatment within defined treatment period. Therefore, if 18 or more subjects are feasible to the treatment at the first stage, 17 additional subjects will be accrued. The null hypothesis of $p \leq 75\%$ will be accepted if the total number of patients feasible to the treatment are 33 or fewer.

After 39 patients are accrued on Cohort 1, we will start accruing patients on Extension Cohort. The 1-year HR clonal evolution rate of 8% from the 12-H-0150 protocol (Cohort 3 + Extension arm) is used as a benchmark for our population. The 1-year HR evolution rate in the 20-H-0033 study currently stands at 3.8%, with a 95% CI of [0, 10%]. Our objective is to achieve a more precise point estimate for the 1-year HR clonal evolution rate. If we increase the sample size to 80 patients total (Cohort 1 + Extension Cohort) and assume that the HR evolution rate will stay at 3.8%, our confidence width narrows to [0, 7.8%], the upper bound of which is below the 8% historical rate, in which case we can more confidently conclude a benefit in the rate of HR clonal evolution. With 39 subjects already accrued in this study, an additional 41 subjects will need to be recruited.

9.4 STATISTICAL METHODS

The planned analyses will be based on the “intention-to-treat” principle and include descriptive statistics on the proportions of feasible patients. The feasibility probability will be estimated using the sample proportion, and its inferences, including confidence intervals and hypotheses testing, will be evaluated using Binomial distributions. Survival analysis for time-to-death and time-to-response will include methods based on the Kaplan-Meier estimates and the Cox Proportional Hazard regression. If it is appropriate, we will consider additional analyses for the primary and secondary endpoints using the analysis of variance, multiple regression and logistic regression models. Graphical tools will be used to display the appropriate estimates (i.e.

Abbreviated Title: Early Initiation of Oral Therapy for Naïve Severe Aplastic Anemia (SAA)

Version Date: 11/05/2025

estimated proportions and the Kaplan-Meier curves) and their corresponding 95% confidence intervals.

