2.3.5 Scientific and Clinical Justification of the Protocol

The current protocol aims to test the risks and benefits of early treatment with orally administered drugs in patients who have delay in receiving standard treatment, a combination of CsA, EPAG and h-ATG. The desirability of more expeditious treatment is based on the pathophysiology of immune aplastic anemia, T cell mediated destruction of hematopoietic stem and progenitor cells leading to a deficit in marrow regenerative function. Both drugs individually have activity in aplastic anemia as single agents [33, 36, 40] and carry low risk safety profiles over the short term. Indeed, the combination of eltrombopag with cyclosporine, without ATG, is currently being tested in a multicenter trial (SOAR trial: NCT02998645).

Appropriate treatment of patients with SAA is often delayed, as most physicians and many hematologists are not familiar with the disease or comfortable with its therapy. As a quaternary referral center for marrow failure, entry of patients to our protocols maybe delayed for logistical reasons. Even when patients can be admitted to the Clinical Center relatively proximate to their diagnosis, institution of effective therapy is often postponed while awaiting results of testing, intravenous catheter placement, or evaluation of complications or comorbidities. During this period, absent definitive therapies, stem and progenitor cell destruction is assumed to be ongoing.

Morbidity and mortality in severe aplastic anemia patient results from severity and duration of pancytopenia. Expeditious commencement of therapy is expected to abbreviate the period of severe pancytopenia with its attendant consequences: infections and treatment of febrile neutropenia, bleeding from ongoing thrombocytopenia, and anemia. Furthermore, rapid institution of treatment should also allow patients who do not respond to medical therapy, or whose response is not optimal, to proceed faster to transplantation options. Shorter periods between diagnosis and bone marrow transplantation have repeatedly been shown to correlate with transplant outcomes [41]. Robust and rapid hematologic recovery has been associated with better survival outcomes [42], and in our experience, complete hematologic responders are less likely to evolve to myelodysplasia or leukemia (unpublished data).

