- Initiation of additional immunosuppressive therapy other than steroids or cyclosporine (if beyond 6 months then mycophenolate mofetil can also be administered per PI discretion in patients who cannot tolerate cyclosporine and who require immunosuppression) or if beyond 2 years, enroll in other available clinical trials.

Pregnancy: This protocol does not enroll patients who are pregnant or women of child-bearing potential unless they are using contraception during the study treatment period (Section 4.3).

Because aplastic anemia is a disease of young adults, if a woman becomes pregnant while participating in the study despite stringent contraception requirements and education by the study team regarding the risks of relapsed aplastic anemia with pregnancy upon study entry and at

Abbreviated Title: Early Initiation of Oral Therapy for Naïve Severe Aplastic Anemia (SAA)

Version Date: 11/05/2025

every landmark visit, patient may remain on study. This limited inclusion of pregnant women on this study permits capture of the secondary endpoint (relapse of aplastic anemia) without exposing the subject/fetus/neonate to study drugs or invasive protocol procedures.

- If a patient becomes pregnant while on study drugs (CSA and/or EPAG), patient will discontinue the medications immediately but may remain on study
- If a patient becomes pregnant during follow-up period and not on any study treatments, patient may remain on study
- No investigational interventions or research procedures will be performed during pregnancy (if landmark visit is due during pregnancy, it will be delayed till after). All clinical decisions about pregnancy management will be made by the patient and the treating physician.
- If a patient relapses with aplastic anemia during pregnancy, no treatment will be provided on study; recommendations will be provided to the local treating physician for clinical management and if pursued any treatment other than supportive care (transfusions), patient will be taken off study
- Blood count monitoring with complete blood counts (CBCs) will be obtained with increased frequency than otherwise indicated, especially in later gestation, to monitor for AA relapse
- Fetus/neonate is not a research subject in this protocol
- No inducements, monetary, or otherwise, will be offered to terminate a pregnancy
- Individuals engaged in the research will have no part in any decisions as to the timing, method, or procedures used to terminate a pregnancy.

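### Section 9.4 names Kaplan-Meier and Cox for time-to-response without saying how death, transplant, other salvage therapy or off-study exit before response is handled; if these patients are censored, the curve can only equal or exceed the true response proportion.

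*Combined protocol and SAP*

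**What the plan says.** Section 9.4 covers two different outcomes in one sentence: "Survival analysis for time-to-death and time-to-response will include methods based on the Kaplan-Meier estimates and the Cox Proportional Hazard regression". It plans to display "estimated proportions and the Kaplan-Meier curves" with 95% confidence intervals, and it places the planned analyses under the intention-to-treat principle. It contains no censoring rule and no competing-risk estimator.

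Section 9.2 lists response as a landmark endpoint, "a) hematological response at 1, 2, 3, 6 and 12 months and yearly thereafter", and follows patients to 60 months so that "long-term disease-free and overall survival can be estimated". Section 7 also ties response to landmarks, requiring "2 of the following values obtained on 2 serial blood count measurements at least one week apart at landmark time points".

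The protocol foresees events that end a patient's chance of responding to the study regimen:

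- Section 2.3.5 expects rapid treatment to "allow patients who do not respond to medical therapy, or whose response is not optimal, to proceed faster to transplantation options".
- Section 9.6 takes patients off study for several reasons, including MDS or AML, a poor-risk clone, and "Initiation of additional immunosuppressive therapy other than steroids or cyclosporine" (with exceptions beyond 6 months and 2 years).
- Overall survival is a secondary endpoint, so deaths are expected to be counted.

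**The concern.** For time-to-death, death is the event. For time-to-response, death before response makes the event impossible, and transplant or other salvage therapy means that any later recovery is not a response to the study regimen. One method sentence cannot serve both outcomes without a rule for these patients.

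The default in most software is to censor at the last on-study date. Kaplan-Meier then treats each censored patient as if he or she would go on to respond at the same rate as those still at risk. For a patient who dies or is transplanted without responding, that is not so. The risk set shrinks while the later responders stay in it, and the estimated response proportion rises.

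What is at stake is the time-to-response curve, which would be shown beside landmark proportions calculated on all treated patients. The two could disagree at the same month for no reason other than the estimator.

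**Working it through.** The documents state no figure for time-to-response, so there is none to reproduce. The check asks how far one minus Kaplan-Meier (1-KM) departs from the true response proportion when competing events are censored.

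**Inputs**

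- R, the true proportion responding by month 6. Section 2.3.7 prints overall response of 80% (Standard) and 83% (Early). The printed CR and PR do not add to these (40 + 33 = 73; 50 + 40 = 90), so the overall figures are used as printed.
- C, the proportion with a competing event before response. The documents give none, so 2%, 5% and 10% are assumed.
- n = 80 for the simulation (Section 9.3, both cohorts together).

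**Formulas**

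- Cumulative incidence of response at month 6 equals R.
- If the hazards of response and of the competing event stay in constant proportion, 1-KM = 1 - (1 - R - C)^(R/(R + C)).
- Lower bound: if every competing event comes after the last response, 1-KM = R and the excess is zero.
- Upper bound: if every competing event comes at time zero, 1-KM = R/(1 - C).

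**Results for R = 80%**

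| C | 1-KM, proportional hazards | Excess (points) | Upper bound | Range of excess (points) |
|---|---|---|---|---|
| 2% | 1 - 0.18^(0.80/0.82) = 81.2% | 1.2 | 0.80/0.98 = 81.6% | 0 to 1.6 |
| 5% | 1 - 0.15^(0.80/0.85) = 83.2% | 3.2 | 0.80/0.95 = 84.2% | 0 to 4.2 |
| 10% | 1 - 0.10^(0.80/0.90) = 87.1% | 7.1 | 0.80/0.90 = 88.9% | 0 to 8.9 |

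For R = 83% the excess under proportional hazards is 1.3, 3.5 and 7.7 points.

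**Simulation.** This used n = 80, 4,000 repeats and R = 80%. Responses were assumed at months 1, 2, 3 and 6 in shares of 15%, 25%, 30% and 30%, with competing events uniform over 0 to 6 months. Censoring gave 81.3%, 83.5% and 87.9% for C = 2%, 5% and 10%. Keeping the same patients at risk as non-responders to month 6 gave about 80% in every case.

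**A hand check, and its dependence on timing.** Take 30 of 36 responding (83.3%), with 10 responses assumed at each of months 2, 3 and 6, and k of the 6 non-responders censored at month 4. The Kaplan-Meier proportion without response after month 3 is 16/36, and the month-6 factor is (6 - k)/(16 - k).

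- k = 1: 1 - (16/36)(5/15) = 85.2%
- k = 3: 1 - (16/36)(3/13) = 89.7%
- k = 5: 1 - (16/36)(1/11) = 96.0%

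If responses are instead split 14, 14 and 2, the proportion after month 3 is 8/36 and the factor is (6 - k)/(8 - k), which gives 84.1%, 86.7% and 92.6%. With no responses after month 3, the result is 83.3% for every k.

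**The case against.** The strongest reply is that the plan does not say these patients will be censored. Section 9.4 is silent, invokes intention-to-treat, and says only that the methods will include Kaplan-Meier. An analyst who keeps such patients at risk as non-responders would get an unbiased curve. That stands: the point is conditional on censoring. It does not remove the gap, because the plan leaves the choice open and the usual default is the one that goes wrong.

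It can also be said that early exits may be few. Section 4 enrols patients who lack a suitable matched sibling donor or are not transplant candidates. Section 9.6 does not list transplant by name, and its item on treatment other than CsA and EPAG applies at relapse, hence after response. Section 2.3.5 gives no date for transplant. This stands too: the excess could be close to zero, and the 96.0% case needs 5 of 6 non-responders to leave within three months.

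A reader might infer three stronger things that the documents do not support:

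- **The curve is always pushed up.** Exits after the last response leave it unchanged. Section 9.6 also lists exits, such as loss to follow-up, that need not reflect lack of response.
- **The comparison with 12-H-0150 is biased.** Section 9.2 plans response comparisons with that study, but those reported in Section 2.3.7 are 6-month proportions, which this issue does not touch. Nothing says that time-to-response curves will be compared. If they were, the same estimator could raise both, and the net difference cannot be worked out from the documents.
- **Relapse and clonal evolution carry the same error.** Section 9.4 does not assign Kaplan-Meier to either, so no error is shown there.

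**Conclusion.** The point holds in conditional form. Section 9.4 names an estimator for time-to-response without the rule that decides whether it is valid, while the protocol foresees events that preclude response. If those patients are censored, 1-KM cannot fall below the true response proportion, and it exceeds it whenever responses follow the exits. At an assumed 80% true response, the excess is about 1, 3 or 7 points for 2%, 5% or 10% competing events under proportional hazards, within ranges of 0 to about 2, 4 or 9 points. Those rates are assumptions.

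The reach is limited to the time-to-response curve. Landmark response proportions and the binomial feasibility analysis do not change. The amendment is worth making because it is nearly free and removes a possible disagreement between two displays of the same outcome.

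**What to change.** In Section 9.4, separate the two outcomes:

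1. Keep Kaplan-Meier and Cox for overall survival.
2. Estimate time-to-response by cumulative incidence (Aalen-Johansen), with death and transplant or other salvage therapy before response as competing events. Where follow-up over the window is otherwise complete, keeping these patients at risk as non-responders to the end of the window gives the same answer.
3. State how each off-study reason in Section 9.6 is classed when it occurs before response: competing event or ordinary censoring.
4. Label any Cox model for response as cause-specific.
5. If time-to-response curves are compared with 12-H-0150, use the same estimator there.

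Items 1 to 4 cost SAP wording and standard software. Item 5 needs patient-level dates of death, transplant and salvage therapy from 12-H-0150, so it carries some data work if that comparison is made.
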